TITLE: Preloading with Nicotine Replacement Therapy in Smokers with HIV to Improve Self-Efficacy and Quit Attempts

NCT04994444

V.2. 08/12/2021

Project Title: Preloading with Nicotine Replacement Therapy in People with HIV who Smoke to Improve Self-Efficacy and Quit Attempts

Principal Investigator:

[name]

Co-Investigator:

[name]

Description and Purpose of the Project

Cigarette smoking is more prevalent in persons with HIV (PWH) in the U.S. when compared with the general population and is linked to increased morbidity and mortality in this population. Furthermore, PWH who smoke have increased rates of lung and other smoking-related cancers. PWH who smoke are a particularly challenging group, often reporting high severity of nicotine dependence and low rates of self-efficacy for quitting, both factors related to poor smoking cessation outcomes. Establishing more effective smoking cessation approaches for people with HIV who smoke, particularly those that address low self-efficacy and severe dependence, is a public health priority.

The overall goal of this research project is to examine the feasibility, acceptability, and preliminary efficacy of nicotine replacement therapy preloading (NRT-P) in PWH who smoke, who are struggling with cigarette dependence, urge to smoke (craving) and low self-efficacy as barriers to successful smoking cessation. Sixty participants will be recruited into a 16-week randomized pilot study. Thirty participants (control condition) will receive standard smoking cessation counseling (NRT-S) and will initiate an 8-week course of combination nicotine patch and lozenge (or gum, based on preference) on quit date (week 4), consistent with recommended guidelines based on smoking rate. Thirty participants (active condition) will start NRT patch 3 weeks prior to quit date, followed by an 8-week course of combination nicotine patch and lozenge (or gum, based on preference), initiated on quit date. We will examine dependence, urge to smoke and self-efficacy for quitting prior to and following quit date. We will also examine differences in quit attempts and biochemically validated smoking abstinence between the control and active conditions at weeks 8, 12, and 16.

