This study will be the first to examine the feasibility and initial efficacy of a novel intervention using NRT preloading to improve smoking cessation outcomes in PWH. Given the high prevalence of smoking and the significant morbidity associated with it in PWH, the development of effective strategies to reduce the risks related to smoking in this group is critical. If determined to be effective, this intervention could be readily disseminated in HIV clinics. Our study will provide key information on the potential benefit of NRT preloading in a population that is highly dependent on nicotine and highly vulnerable to smoking-related morbidity and mortality. The results from this project will provide the foundation for a future R01 application to the National Cancer Institute to conduct a full-scale randomized clinical trial.

Aims

The specific aims of this randomized pilot study are:

Aim 1: To examine the feasibility and acceptability of NRT preloading in smokers with HIV. We will examine adherence (percent of days using the patch) to NRT prior to quit date in the preloading condition, and compare adherence after quit date across the standard (NRT-S) and preloading (NRT-P) conditions.

Aim 2: To examine differences in quit attempts and biochemically validated smoking abstinence between the

control and active conditions. We hypothesize that participants in NRT-P, compared to NRT-S, will have higher rates of CO-verified abstinence from smoking at weeks 8, 12 and 16. Cotinine verified abstinence at week 16.

Aim 3: To examine nicotine dependence, self-efficacy for cessation, and urge to smoke (craving) as mediators of abstinence. We hypothesize that participants in NRT-P, compared to NRT-S, will show greater reductions in dependence and urge to smoke, and greater increase in self-efficacy from baseline through quit date, and that these mediators will account for the effect of NRT-P on smoking abstinence at weeks 8 and 12 and 16.

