We will randomize 60 smokers with HIV to either NRT-P or NRT-S using urn randomization¹⁷ to ensure balance on gender and level of cigarette dependence (Fagerström Test of Cigarette Dependence (FTCD) score)¹⁸. Both

conditions will receive the same behavioral counseling support, which will be delivered in 5 sessions over 5 weeks, with the target quit date (TQD) scheduled at week 4. We will include 8 weeks of TNP for those in the ST condition (starting at TQD and continuing for 8 weeks) or 11 weeks of TNP for those in the NRT-P condition (starting 3 weeks prior to TQD). Dosage of TNP in each condition will be based on smoking rate and level of nicotine dependence at baseline (BL). All participants will also be provided with 8 weeks of nicotine lozenge or gum (started on TQD) and will be encouraged to use them every 1-2 hours to manage cravings and urge to smoke, with a goal of using at least 5 lozenges or gum daily. This instruction has been used in previous studies of this type and been shown to be beneficial^{19,20}. Smoking outcomes (7-day CO-verified point prevalence abstinence) will be assessed at 4, 8-, and 12-weeks after the TQD (Weeks 8, 12, and 16). Cigarettes per day, FTCD, urge to smoke, and self-efficacy for quitting will be collected at Baseline, and at 2- weeks after Baseline. We will compare NRT-P and NRT-S on adherence to pharmacotherapy (percent days using patch), smoking cessation rates, study retention and study satisfaction. We will calculate a preliminary effect size estimate of NRT-P on smoking and other secondary outcomes, and mechanisms of change. See Study Flow Diagram below.

Figure 1. Study Flow Diagram.

Recruitment and Participant Population

We will recruit participants (N=60) from the Providence community, the Miriam Immunology Center (MIC) in Providence, RI, and on social media (such as Facebook, Craigslist, Today@ Brown, Share lab website). Study information will be posted on the Share lab website at Brown. Study flyers will be posted on MIC bulletin boards, in the Providence community, and at AIDS-service organizations.

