Timeline Followback (TLFB) is a calendar-assisted structured interview designed to cue memory so that accurate recall is enhanced. The TLFB has established reliability and validity for smoking. The TLFB will be used to assess adherence to nicotine patch, all forms of tobacco use, marijuana use, and self-reported smoking for 7 days prior to baseline and week 2 visit, and for 7 days prior to each follow-up session at weeks 8, 12, and 16.

The Self-efficacy for Smoking Cessation Scale, which has shown good psychometric properties and excellent predictive validity, will be assessed at baseline, weeks 2, 4, 8, 12, and week 16.

Urge to smoke will be assessed at baseline and at weeks 2, 4, 8, 12, and 16 follow-up assessments using the Brief Questionnaire of Smoking Urges (B-QSU). This well-validated measure includes 10 items which assess urges to smoke for either positive reinforcement or negative reinforcement.

Biochemical Verification. All participants will provide breath samples for exhaled CO testing at baseline and at follow up sessions with the RA, at weeks 2, 4, 8, 12, and 16.

Other Measures

1. session attendance after baseline (continuous variable, range 1-6 study sessions);
2. retention (dichotomous variable, participants who complete the 16-week session with the RA will be characterized as completers, those not attending the final session as non-completers);
3. Smoking Situations Confidence scale, to measure self-efficacy for smoking cessation;
4. Readiness to Quit, using the Contemplation Ladder;
5. Treatment Satisfaction scale (CSQ-8).
6. Minnesota Nicotine Withdrawal Scale, to measure nicotine withdrawal symptoms. To be administered at weeks 4, 8, 12, and 16.
7. Commitment (to Quit) Scale, to be administered at baseline and week 4.
8. Quit Attempts (1-item) questionnaire, to measure quit attempts at weeks 4, 8, 12, and 16;
9. Anhedonia scale (3-item scale) at baseline, weeks 2, 4, 8, 12, and 16.
10. Medication Adherence Calendar, at weeks 4 (in active condition only), weeks 8 and 12.
11. Brief Qualitative Interview. An interview agenda will be utilized to explore perceptions of using psilocybin for smoking cessation in a future study. This is an opt-in procedure for current (at week 12 or week 16) and past study participants.

Analytic Plan.

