Assessments will be designed as Qualtrics surveys and paper surveys. Qualtrics will be used for all data collection. If Qualtrics is unavailable, the RA may use paper surveys for data collection. The data will then be transferred into Qualtrics. Data will be verified, checked, and uploaded to an SPSS file to conduct analyses. Initial data analysis will include distribution properties of baseline variables, and correlations among outcome measures.

Data Analysis. Initial data analysis will include examination of BL characteristics by condition, distribution properties of dependent and other variables, patterns of missing data by condition and correlations among outcome measures. **Sample Size and Power Considerations.** Our primary objective will be to examine preliminary effect sizes for NRT-P, rather than to determine statistical significance between groups at certain p values. At the same time, we are well aware of the dangers of relying exclusively on small-scale pilots to determine the promise of novel treatment approaches¹⁰¹. These effect size estimates have a large standard error, and we primarily will be hoping to find a pattern of results that is supportive of the experimental treatment. Effect size estimates will include odds ratios for smoking abstinence. We believe a sample size of 60 should allow adequate examination of NRT-P intervention effect sizes while staying within the scope of a developmental project. We recognize that only large effect sizes will be likely to attain statistical significance with a sample of this size, and large effect size are not anticipated. Our data also will allow us to obtain stability estimates for point-prevalence abstinence (i.e., intercorrelations among outcomes at 4 and 12 weeks). Using a program that allows us to specify proportions at each time point and the correlations between time points¹⁰², we will be able to get a good estimate of the sample size needed to find a significant main effect of treatment in a repeated measures analysis using generalized estimating equations^{103,104}. All analyses will include sex as a covariate, and follow-up analyses will test the Sex x Condition interaction to determine whether sex moderates the effects.

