Treatment Feasibility, Acceptability, & Efficacy (Aims 1 and 2). We will first examine percent adherence to NRT prior to quit date in the NRT-P condition. We will then use t -tests to compare conditions on percent days adherent to NRT after TQD, and number of counseling sessions attended, and client satisfaction scores. We will compare side effects and NRT discontinuation rates between the active and control conditions. For treatment retention rate (dichotomous), a chi-square analysis will be used. Analyses of Aim 2 will test the hypothesis that NRT-P improves point prevalence abstinence relative to NRT-S. Tests of the effect of treatment condition on 7-day point-prevalence abstinence across the 8-, and 12-week assessments will be conducted using GEE, which provides appropriate modeling of covariance structures when observations are correlated across time⁸². The primary, between groups, independent variable in the GEE analysis is treatment condition assignment, which will be dummy-coded using NRT-S as the reference group. Following the intention-to-treat principle, all participants who have been randomized will be included in the analyses.

Potential Mechanisms of NRT-P Effects. Sample size in this pilot trial precludes formal mediation analysis with adequate power. The analyses are designed to test the plausibility of potential mechanisms of the NRT-P treatment effect. We will first run regression analyses predicting the putative mediators (nicotine dependence, self-efficacy for cessation, and urge to smoke) at both week 2 (1 week after those in NRT-P have initiated preloading) and week 4 (TQD) with treatment assignment and the BL value of the respective outcome as predictors. We will then enter change in the mediators from BL to week 2 and week 4 in the GEE models of smoking abstinence. Due to limited sample size, each mediator will be examined separately. We will examine

whether the effect of treatment is reduced when the mediator is added to the model and can test for significance (not expected given the sample size) using the products of coefficients method¹⁰⁵.

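### The Aim 2 abstinence model names two assessments on an unstated clock, while Aims 2 and 3 hypothesise on three (study weeks 8, 12 and 16)

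*Combined protocol and SAP*

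**What the plan says.** Three assessments of abstinence are set consistently outside the Analytic Plan.

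- Description and Purpose of the Project promises to examine "differences in quit attempts and biochemically validated smoking abstinence between the control and active conditions at weeks 8, 12, and 16".
- Aim 2 hypothesises that the preloading arm "will have higher rates of CO-verified abstinence from smoking at weeks 8, 12 and 16".
- Aim 3 hypothesises that the mediators will "account for the effect of NRT-P on smoking abstinence at weeks 8 and 12 and 16".
- Study Methods gives both clocks together: smoking outcomes "will be assessed at 4, 8-, and 12-weeks after the TQD (Weeks 8, 12, and 16").

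The Analytic Plan differs. Under Treatment Feasibility, Acceptability, & Efficacy (Aims 1 and 2), the model sentence is: "Tests of the effect of treatment condition on 7-day point-prevalence abstinence across the 8-, and 12-week assessments will be conducted using GEE". Two assessments are named and no time origin is given. Under Potential Mechanisms of NRT-P Effects, changes in the mediators are entered into the same GEE models. Under Sample Size and Power Considerations, the stability of abstinence is to be estimated from "intercorrelations among outcomes at 4 and 12 weeks", again with no time origin.

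**The concern.** The stated primary objective is to estimate preliminary effect sizes, including odds ratios for abstinence, rather than to test significance. In an estimation study, the visits that the model averages over are part of the definition of the effect. Here the one sentence that defines the efficacy model disagrees with the hypotheses it serves and can be read in two ways. The visit set could therefore be settled after the data are seen.

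The two readings do not have equal consequences. Study Methods gives the control arm 8 weeks of patch, "starting at TQD and continuing for 8 weeks", and both arms have the same 8-week post-quit course. If the GEE weeks are study weeks, the omitted visit (week 16) is the only one clearly after that course. It is also the visit for which Aim 2 names cotinine verification. If they are weeks after TQD, the omitted visit (study week 8) falls during treatment and the consequence is milder.

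The pilot is also meant to inform the size of a full trial, from proportions at each time point and correlations between time points. That calls for all three visits and all three pairwise correlations.

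**Working it through.** The plan has no power calculation to reproduce: 60 participants is justified by the scope of a developmental project. The check is therefore a comparison of visit sets, followed by an illustration of size.

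**1. Clock conversion.** TQD is at study week 4 (Study Methods), so study week = 4 + weeks after TQD. Then 4 + {4, 8, 12} = {8, 12, 16}, and the two-clock statement in Study Methods is internally consistent. The 8-week course ends at 4 + 8 = week 12.

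**2. Visits hypothesised but not modelled.**

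| Reading of the GEE sentence | Study weeks modelled | Omitted from {8, 12, 16} |
|---|---|---|
| Weeks from baseline | 8, 12 | 16 |
| Weeks from TQD | 12, 16 | 8 |

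One visit is missing either way. Because missing abstinence data count as smoking, every randomised participant contributes at every modelled visit: 60 × 3 = 180 person-visits against 60 × 2 = 120.

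**3. Which clock?** The text does not settle it. Study Methods writes the post-TQD weeks with the same odd hyphen and comma, which suggests that the GEE sentence lost its first entry. The 4-and-12-week wording in the sample-size paragraph also fits the post-TQD clock, since study week 4 is the TQD itself and not an abstinence assessment. Against that, the paragraph after the GEE sentence counts in study weeks, with week 4 identified as TQD.

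**4. Precision (assumed equal correlation r between visits; the documents give none).** The variance of an equally weighted mean, relative to one visit, is (1 + 2r)/3 for three visits and (1 + r)/2 for two.

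| r | Three visits | Two visits | SE ratio, two to three | Information lost |
|---|---|---|---|---|
| 0.4 | 0.600 | 0.700 | 1.080 | 14.3% |
| 0.5 | 0.667 | 0.750 | 1.061 | 11.1% |
| 0.7 | 0.800 | 0.850 | 1.031 | 5.9% |
| 0.8 | 0.867 | 0.900 | 1.019 | 3.7% |

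For scale, assume 20% abstinence in the control arm and an odds ratio of 2 (33.3% in the active arm), with 30 per arm. The one-visit variance of the log odds ratio is 1/(30 × 0.2 × 0.8) + 1/(30 × 0.333 × 0.667) = 0.208 + 0.150 = 0.358. Multiplying by the factors above and taking the square root:

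| r | SE, three visits | 95% CI | SE, two visits | 95% CI |
|---|---|---|---|---|
| 0.4 | 0.464 | 0.81 to 4.96 | 0.501 | 0.75 to 5.34 |
| 0.8 | 0.557 | 0.67 to 5.96 | 0.568 | 0.66 to 6.09 |

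**5. Dependence of the estimate on the reading.** The pooled odds ratio is approximated by the geometric mean of assumed visit-specific odds ratios; this is not a GEE fit.

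| Assumed OR at weeks 8, 12, 16 | All three | Weeks 8 and 12 | Weeks 12 and 16 |
|---|---|---|---|
| 2.0, 2.0, 2.0 | 2.00 | 2.00 | 2.00 |
| 2.2, 2.0, 1.8 | 1.99 | 2.10 | 1.90 |
| 2.5, 2.0, 1.5 | 1.96 | 2.24 | 1.73 |

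For the last row: (2.5 × 2.0 × 1.5)^(1/3) = 1.96, (2.5 × 2.0)^(1/2) = 2.24 and (2.0 × 1.5)^(1/2) = 1.73.

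**The case against.** The best defence is that this is a typing slip. Restore a missing 4 to the list, count from TQD, and the GEE covers exactly the visits in Study Methods. Even without that repair, the post-TQD reading has good support and keeps the final visit in the model, so the more serious consequence disappears. The project description and Study Methods already promise comparisons of abstinence that include week 16. The sample-size paragraph speaks of odds ratios in the plural without tying them to this GEE. The numerical effect is also small: the pooled values in the last table, from 1.73 to 2.24, all lie well inside a three-visit confidence interval of 0.81 to 4.96. The data will be collected, so nothing is irrecoverable.

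Much of this stands. A slip is the likely explanation, the precision loss is minor, and the differences between readings are small against the sampling error of a 60-person pilot. But it speaks to what was probably intended. As written, neither clock gives three visits. No other section adds the third to the model, and this GEE is the only model named that yields a condition effect on abstinence. A general promise to examine week 16 does not say how it enters the analysis.

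**Conclusion.** The concern holds and should be fixed. The GEE sentence covers two of the three hypothesised visits on either clock, and the Aim 3 models inherit the mismatch. This part rests on the text alone and needs no assumption.

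The size of the consequence does rest on assumptions. With equal correlations of 0.4 to 0.8, the standard error is 8% to 2% larger with two visits than with three. The point estimate depends on the reading only if the effect changes over time: not at all for a constant odds ratio, 1.90 to 2.10 for a mild decline, and 1.73 to 2.24 for a steeper one. The main defect is an undefined estimate for a primary objective; lost precision is secondary.

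A separate, lesser gap, on which this conclusion does not rely, concerns quit attempts. They appear in the title and Aim 2 and are collected with the "Quit Attempts (1-item) questionnaire, to measure quit attempts at weeks 4, 8, 12, and 16", yet the Analytic Plan names no between-group analysis of them.

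**What to change.** 1. In the GEE sentence, replace the two named assessments with: study weeks 8, 12 and 16 (4, 8 and 12 weeks after TQD). Report the overall odds ratio for condition from that model. The odds ratio at each week, reported descriptively, would be a useful addition because it shows whether the effect changes after NRT ends.
2. Under Potential Mechanisms of NRT-P Effects, state that the abstinence models use the same three visits.
3. Under Sample Size and Power Considerations, replace the 4-and-12-week correlation with the three pairwise correlations among study weeks 8, 12 and 16.
4. Add one sentence naming a between-group analysis of quit attempts at the weeks they are collected (4, 8, 12 and 16), using the item's own recall period.

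The cost is wording only. Self-reported smoking by Timeline Followback and exhaled CO are already scheduled at weeks 8, 12 and 16, and the quit-attempt item at all four of its weeks. No visit, measure or participant is added. The change should be dated and made before outcomes are compared by arm; if that comparison has already been made, the report should say so.

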| Week 2 | Research Assistant | 20 minutes | surveys | \$20 |
| Week 2 | Nurse (In-person, phone call or Zoom) | 30 minutes | Counseling | None |
| Week 4 | Research Assistant | 20 minutes | Surveys, blood pressure, breath test | \$20 |
| Week 5 | Nurse (phone call) | 20-30 minutes | Counseling | None |
| Week 6 | Nurse (phone call) | 20-30 minutes | Counseling | None |
| Week 8 | Research Assistant | 20 minutes | Surveys, blood pressure, breath test | \$25 |
| Week 12 | Research Assistant | 20 minutes | Surveys, blood pressure, breath test | \$25 |
| Week 16 | Research Assistant | 20 minutes | Surveys, blood pressure, breath test | \$50 |
| Week 12 OR Week 16 | Research Assistant | 20 minutes | Brief Qualitative Interview | \$10 |

Brief Qualitative Interview.

An open-ended interview will be completed at the Week 12 or Week 16 study visit, or as an additional, optional session for participants who have already completed their final study session. The qualitative interview will ask about participants' perspectives and opinions on using psychedelics, specifically Psilocybin, for smoking cessation.

Pharmacotherapy.

Nicotine Patch, Lozenge & Gum.

All participants in the NRT-S condition will receive an 8-week course of transdermal nicotine patch (TNP) and nicotine lozenge or gum. Participants will be provided with an initial 4-week supply of patch and lozenge or gum at their Week 1 session with the nurse in anticipation of their TQD, and will be instructed to start using the TNP on the morning of their quit date.

NRT Dosing.

Participants will use a 21 mg patch for 4 weeks, followed by 2 weeks of 14 mg and 2 weeks of 7 mg; those participants smoking 5-10 cigarettes a day will start with the 14 mg patch.

Participants will be instructed to use lozenges (2mg each) or gum consistent with the package insert labeling: one every 1-2 hours and up to 12 daily. They will be advised to use at least 5 lozenges or gum daily.

At the week 8 visit, participants will receive instructions for patch tapering and be provided the needed 14 mg and 7 mg patches.

Possible side effects, which are typically mild, will be explained and participants will be urged to contact study staff if they have questions. Participants who discontinue the patch or lozenge early will be retained in the study.

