In addition to the pharmacotherapy procedure described above, participants in the NRT-P condition will be provided with a 21mg TNP for 3 weeks prior to the QD (started during the first session with the nurse). This course of pre-loading will be followed by the same 8-week course of TNP/lozenge started on the target quit date as described above.

Study Safety Monitoring

Adverse effects of NRT are infrequent and tend to be minor. The most common discomfort from NRT is skin irritation. Participants will be advised to rotate the site of the NRT patch each day when it is changed. A

Nicotine Patch Information Sheet will be provided to each participant. Participants will be asked to contact study staff in the event of any unexpected reaction. The RA will contact the study medical provider ([name], PI) regarding any adverse events within 24 hours. In these cases, participants will be contacted by [name] and may be advised to stop using the NRT.

Compensation. Total possible compensation \$210: \$40 for the baseline assessment; \$20 for the nurse visit at week 1, \$20 for the week 2 assessment, \$20 for the week 4 assessment, \$25 for the week 8 assessment, and \$25 at week 12, and \$50 at week 16.

Ten dollars (\$10) compensation will be given for completion of the qualitative interview. Participants can now receive up to \$210 compensation for completing the entire study.

Participants will receive compensation only for the sessions they complete. Compensation will not be contingent upon smoking status.

ClinCard. Payment for participating in this study will be made using the ClinCard, a pre-paid card that works like a bank debit card. Each participant will be issued one card for the duration of their participation. They will be given the ClinCard information sheet about how to use this card and who to call if they have any questions. Money will be added to their card according to the study's payment schedule. They may use this card at any store that accepts Mastercard. They may also use an ATM with the Mastercard logo to withdraw cash. If they use the card to withdraw cash, or if the card is not used within any six (6) month period, they will be charged a fee that will reduce the total amount of money left on the card. Please ask them to read the FAQ information sheet that the RA will give them at the Baseline appointment for full details about fees.

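### The abstinence GEE gives one condition effect across visits and no modelled effect at week 16, the only abstinence visit after the NRT course ends

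*Combined protocol and SAP*

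**What the plan says.** **Hypothesis.** Under Aims, Aim 2 expects that NRT-P participants "will have higher rates of CO-verified abstinence from smoking at weeks 8, 12 and 16". It also lists cotinine-verified abstinence at week 16. The project description likewise promises abstinence comparisons at weeks 8, 12 and 16. Neither place gives a method.

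**Model.** The section Treatment Feasibility, Acceptability, & Efficacy (Aims 1 and 2) tests the effect of condition on 7-day point-prevalence abstinence by GEE across the 8- and 12-week assessments. It does not say whether those weeks count from baseline or from the target quit date (TQD). It continues: "The primary, between groups, independent variable in the GEE analysis is treatment condition assignment, which will be dummy-coded using NRT-S as the reference group". Sex is a covariate in all analyses, and Sex x Condition is the only interaction planned.

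**Calendar.** Study Methods describes counseling "with the target quit date (TQD) scheduled at week 4" and places the abstinence assessments 4, 8 and 12 weeks after TQD, which are study weeks 8, 12 and 16. Under Pharmacotherapy: "All participants in the NRT-S condition will receive an 8-week course of transdermal nicotine patch (TNP) and nicotine lozenge or gum". For NRT-P: "This course of pre-loading will be followed by the same 8-week course of TNP/lozenge started on the target quit date".

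**Future trial.** Sample Size and Power Considerations aims to estimate the sample size needed to "find a significant main effect of treatment in a repeated measures analysis using generalized estimating equations", using an abstinence proportion for each time point and the correlations between time points.

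**The concern.** Preloading is given before the quit date, and after it both arms are offered the same NRT. Whether any advantage outlasts the NRT course is therefore a central question for this pilot, and only week 16 can inform it. A single condition coefficient cannot show whether the effect holds, fades or grows over visits, so the stated model does not match a hypothesis stated for each visit.

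The risk is in interpretation. If preloading helps early and the benefit has gone by week 16, the one odds ratio the model yields can still lie above 1, and no planned model output would show the fading. Effect-size estimation is the stated primary objective, so that odds ratio is a main product of the study.

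**Working it through.** **1. Which visits are off NRT.** TQD is week 4, and 4 + 8 = 12. The patch schedule under NRT Dosing gives the same length: 4 + 2 + 2 = 8 weeks. Post-quit NRT ends at week 12 in both arms. Week 8 is on NRT, week 12 is at its end and week 16 is off it.

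**2. What the GEE can contain.** There are three readings:
- Study weeks 8 and 12: no off-NRT visit.
- 8 and 12 weeks after TQD, which are study weeks 12 and 16: one visit at the end of NRT and one off it.
- Extended to Aim 2: weeks 8, 12 and 16.

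The sample-size section mentions correlations between outcomes at 4 and 12 weeks. That fits counting from TQD, because no abstinence outcome is listed at study week 4, but it does not settle the matter.

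**3. First illustration.** The documents give no abstinence rates, so all rates here are assumed. NRT-S: 20%, 17%, 15%. NRT-P: 35%, 22%, 15%, at weeks 8, 12 and 16.
- Week 8: (0.35/0.65)/(0.20/0.80) = 2.15
- Week 12: (0.22/0.78)/(0.17/0.83) = 1.38
- Week 16: 1.00

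Odds ratio from the mean rates under each reading:

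| Visits | NRT-S mean | NRT-P mean | Pooled OR |
|---|---|---|---|
| Weeks 8, 12 | 18.5% | 28.5% | (0.285/0.715)/(0.185/0.815) = 1.76 |
| Weeks 12, 16 | 16.0% | 18.5% | (0.185/0.815)/(0.160/0.840) = 1.19 |
| Weeks 8, 12, 16 | 17.3% | 24.0% | (0.240/0.760)/(0.173/0.827) = 1.51 |

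**4. Second illustration: the effect stops when NRT stops.** Control abstinence is assumed to be 30%, 25% and 20%, with true OR 2 at weeks 8 and 12 and 1 at week 16. NRT-P rates follow from OR x p/(1 - p + OR x p): 46.2%, 40% and 20%. The large-sample value of a logistic model with visit terms and one condition term is 2.0 for weeks 8 and 12, 1.49 for weeks 12 and 16, and 1.67 for all three. Over three assumed control profiles, with rates between 10% and 30%, the two readings that include week 16 give 1.46 to 1.70. With a true on-NRT OR of 3 they give 1.85 to 2.37.

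**5. How this looks with 30 per arm.** This used the base scenario of step 4 with an exchangeable GEE, 300 simulated trials per setting, latent inter-visit correlation 0.6 or 0.8, two-sided 5% tests and no sex covariate.

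| Visits | Estimated OR above 1 | Significant benefit | Condition-by-visit p < 0.05 |
|---|---|---|---|
| Weeks 8, 12 | 92-95% | 31-34% | 5% (no true interaction) |
| Weeks 12, 16 | 81-83% | 13-14% | 18-22% |
| Weeks 8, 12, 16 | 89-90% | 24-26% | 18-19% |

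**6. Precision.** For one visit, SE(log OR) = sqrt(2/(30 p(1 - p))): 0.72 at p = 0.15 and 0.60 at p = 0.25. Averaging three visits with assumed correlation 0.55 multiplies this by sqrt((1 + 2 x 0.55)/3) = 0.84, giving 0.60 and 0.50. A single-visit interval is thus 1/0.84 = 1.2 times as wide on the log scale.
- Week-16 OR of 1 at 15% per arm: exp(±1.96 x 0.72), about 0.24 to 4.1.
- Week-16 OR of 1 at 20% per arm (SE 0.65): about 0.28 to 3.5.
- Pooled OR of 1.51 with SE about 0.54: about 0.5 to 4.3.

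**The case against.** Several stronger conclusions are tempting, and the documents do not support them.

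- *The model averages visits on and off NRT.* Not established. Read as study weeks, the GEE has no off-NRT visit, and the fault is the absence of week 16 rather than averaging.
- *A vanished effect would be reported as a benefit.* Too strong. The plan aims at effect sizes, acknowledges their large standard error and expects no large effects. A pooled OR of 1.51 would carry an interval of about 0.5 to 4.3, and under the readings that include week 16 most simulated trials were not significant.
- *No week-16 result is planned.* The project description and Aim 2 both plan one, including cotinine verification. What is missing is a method.
- *The next trial would be sized from one pooled odds ratio.* The planning paragraph uses proportions at each time point, so fading can enter there, although its target is a main effect.
- *NRT exposure after the quit date confounds the comparison.* It does not. Both arms stop at the same time, so the issue is an effect that may change over time.

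It is also fair to say that a main-effect GEE is conventional, that naming condition as the primary variable does not exclude a visit term, and that in the first illustration most of the decline comes before NRT ends. The visit-level estimate will be imprecise.

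What stands is that no reading of the plan yields a modelled week-16 effect. Lack of significance gives limited protection when the estimate itself is the product. Imprecision is a reason to show the interval, not to leave the estimate out.

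**Conclusion.** The point holds in limited form. The stated GEE yields one condition effect, does not match Aim 2's visit-specific hypothesis and provides no modelled estimate at the only off-NRT abstinence visit. If the benefit has gone by week 16, the main-effect OR could still be above 1: 1.19 to 1.76 in the first illustration and 1.49 to 2.0 in the second, depending on which visits enter. These figures rest on assumed rates and show direction and rough size only. The gap should be closed before analysis. It does not undermine the design or the comparison of arms.

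**What to change.** Amend the analytic plan as follows:

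1. Name the GEE visits as study weeks 8, 12 and 16, in line with Aim 2.
2. Include visit as a categorical term and condition-by-visit, with sex as already planned.
3. Report the OR and risk difference with 95% interval at each visit, and identify week 16 as the off-NRT estimate.
4. Keep the average condition effect as a summary.
5. Do not use the interaction p-value to decide whether the effect is constant. At this sample size it detected the assumed change in only 18-22% of simulated trials with an on-NRT OR of 2.
6. Describe any statement on lasting abstinence as preliminary and based on the week-16 estimate and its interval.

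The cost is revised wording and one more table. Visit-level intervals are about 20% wider than the pooled one, and the week-16 OR interval would run from roughly 0.25 to 4 at 15-20% abstinence per arm. No new data are needed.
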